## 7 General Considerations

Datasets submitted to regulatory agencies will be created according to Clinical Data Interchange Standards Consortium (CDISC) standards. Submission data will be provided in Study Data Tabulation Model (SDTM) format. Analysis data will be provided in Analysis Data Model (ADaM) format.

Statistical Analysis System (SAS) version 9.4 or higher will be used to perform all data analyses.

Continuous variables will be summarized in terms of the number of observations (n), mean, SD, median, first quartile, third quartile, minimum and maximum. Other descriptive statistics (e.g., standard error [SE], CV%) may be reported when appropriate. For repeated assessments of continuous variables, the change from baseline will also be summarized. Categorical variables will be summarized using frequency counts and percentages. Analyses that use other descriptive statistics will have the specific descriptive statistics identified with the analysis in the applicable SAP section.

Statistical tests will be 1-sided and will be performed at an alpha level of 0.025 unless otherwise stated.

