### 10.1.3.1 Tipping Point Analysis

Missing primary efficacy outcome is defined as subjects with less than 28 days of the Treatment Period and without documented tracheal intubation or death. Missing primary efficacy outcome will be imputed in a systematic way as having or not having experienced the event, where the event is progression to tracheal intubation or death prior to tracheal intubation.

The purpose of the tipping point analysis is to show which combination of imputed values for the missing primary efficacy outcome may alter the result of the primary efficacy comparison. Thus, the tipping point analysis will only be performed if the primary efficacy analysis indicates a significant treatment effect.

Analyses will be run for each possible combination of missing outcomes considering the subjects as not interchangeable: for each subject with missing outcome the two possible outcomes (1 = having experienced the event, 0 = not having experienced the event) will be imputed in combination with every other subject with missing outcome with the two possible outcomes of these subjects. This will result in  $2^m$  possible combinations, with  $m$  being the number of subjects with missing outcome in both treatment group combined. All combinations of imputed data will be analyzed with the primary model as specified in Section 10.1.2.

The possible combinations will be derived as illustrated below for up to 4 subjects:

[figure not shown]
Number of Subjects With Missing Outcome	Possible Combinations* (Number of Analyses)	Proportion of Subjects Experiencing the Event
1	2 (0, 1)	0, 1
2	4 (00, 01, 10, 11)	0, 0.5 (twice), 1
3	8 (000, 001, 010, 011, 100, 101, 110, 111)	0, 0.33 (three times), 0.67 (3 times), 1
4	16 (0000, 0001, 0010, 0011, 0100, 0101, 0110, 0111, 1000, 1001, 1010, 1011, 1100, 1101, 1110, 1111)	0, 0.25 (4 times), 0.5 (6 times), 0.75 (4 times), 1

0 = subject did not experience the event, 1 = subject experienced the event

The treatment comparisons obtained from each combination will be classified into favorable (1-sided p-value < 0.025 symbolized by black color) and unfavorable (1-sided p-value ≥ 0.025 symbolized by red color) and depicted in a graph where the x-axis and y-axis will present the proportion of subjects with missing endpoint imputed as having experienced the event for CSL312 + SOC and placebo + SOC, respectively.

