If each subject with missing outcome is combined with every other subject with missing outcome, there will be more than one combination with the same proportion of subjects having experienced the event if  $m > 1$  as illustrated in the last column of the above table. The median p-value of the combinations with the same proportion of subjects having experienced the event will be used in the graph.

An example for such a graphical display could look like this (the axes represent the number of missing subjects in this graph, but maybe translated to the proportion of subjects having or not having experienced the event):

Red: 1-sided p-value ≥ 0.025, black: 1-sided p-value < 0.025

The number of subjects with missing outcome in this study is expected to be small. However, if the number of subjects with missing outcome is large and all possible  $2^m$  combinations become too cumbersome for above described method to be implemented, an alternative method will be used (e.g., if appropriate, treating subjects as interchangeable, i.e., no covariates besides treatment will be included in the logistic regression model and there will

be  $(a+1)*(b+1)$  combinations for possible outcomes where a and b are the number of subjects with missing outcome in each treatment group, respectively).

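### SAP 10.1.3.1 groups tipping-point imputations by a proportion that reads as pooled over both arms but plots them on per-arm axes; taken literally, the worst-case corner gets too small a p-value

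*SAP*

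**What the plan says.** SAP 10.1.3.1 runs the primary model on all 2^m imputations of the missing primary outcomes, with m "being the number of subjects with missing outcome in both treatment group combined". A table for m = 1 to 4 lists the combinations and the resulting event proportions. The row for m = 4 reads "0, 0.25 (4 times), 0.5 (6 times), 0.75 (4 times), 1", with no split by arm.

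Each comparison is coloured black (one-sided p below 0.025) or red (otherwise). The two axes of the graph are "the proportion of subjects with missing endpoint imputed as having experienced the event for CSL312 + SOC and placebo + SOC, respectively".

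The section then says that several combinations share a proportion once m exceeds 1, "as illustrated in the last column of the above table", and gives the display rule: "The median p-value of the combinations with the same proportion of subjects having experienced the event will be used in the graph". If m is too large, a simpler method is allowed with (a+1)*(b+1) outcomes, "where a and b are the number of subjects with missing outcome in each treatment group, respectively".

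The analysis is run only if the primary result is significant.

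**The concern.** The point is which combinations are merged before the median is taken. The text leading to the rule defines a proportion over all m missing subjects. The graph needs one value for each pair of per-arm proportions. These are different groupings. Under the first, a CSL312 subject imputed as an event and a placebo subject imputed as an event count as the same thing, although they lie at opposite corners of the graph.

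The graph exists to show which imputations overturn a significant result. The most important one is the asymmetric corner, and no other planned analysis shows it. The primary analysis (SAP 10.1.2) sets missing outcomes to non-event in both arms, one sensitivity analysis (SAP 10.1.3) sets them to event in both arms, and the complete-case analysis leaves them out. If this corner is drawn with a value borrowed from more favourable cells, the plan has no other place where the reader would see the problem.

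**Working it through.** **1. Reproduce the table.** Grouping the 2^m strings of 0s and 1s by total events gives group sizes C(m,k). For m = 4 these are 1, 4, 6, 4, 1, exactly as printed, and the other rows also reproduce. Grouping by arm does not give this: four missing subjects split 2+2 form nine cells of sizes 1, 2, 1, 2, 4, 2, 1, 2, 1. The printed sizes match per-arm cells only if all missing subjects are in one arm.

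**2. Check the sentence on m > 1.** With one missing subject per arm, m = 2. There are four graph cells holding one combination each, so nothing is duplicated. The sentence is true for this case only if the proportion is pooled.

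**3. Size of the merged group.** With a missing in CSL312 and b in placebo, the worst corner (a, 0) is one combination. Its pooled proportion a/(a+b) is shared by C(a+b, a) combinations: 2 for 1+1, 6 for 2+2, 20 for 3+3, 70 for 4+4. Every other member has fewer CSL312 events and more placebo events. In a treatment-only model each therefore has a smaller p-value, and so does the median.

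**4. Method for the illustrations.** Inputs are 62 per arm (SAP 4.4) and the one-sided 0.025 threshold (SAP 7). Event counts and missing counts are assumptions, because the SAP gives no missing-data rate and says only that few are expected. Observed events exclude the missing subjects, who count as non-events in the primary analysis. The model is Firth logistic regression with treatment only. With x1 and x2 events, the fitted rates are (x+0.5)/63, the common null rate is (x1+x2+1)/126, and the one-sided p is 1 − Φ(√LR), where LR is the penalised likelihood-ratio statistic.

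**5. 8 v 18 events, one missing per arm (primary p = 0.0142).**

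| CSL312 imputed events | Placebo imputed events | Own p | Plotted under pooling |
|---|---|---|---|
| 0 | 0 | 0.0142 | 0.0142 |
| 0 | 1 | 0.0086 | 0.017 |
| 1 | 0 | 0.0261 | 0.017 |
| 1 | 1 | 0.0164 | 0.0164 |

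The two middle rows share pooled proportion 0.5; their median is (0.0086 + 0.0261)/2 = 0.017. The only red cell turns black, and so the whole graph is black.

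**6. Other assumed scenarios.**

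| Events | Missing (CSL312, placebo) | Worst corner, own p | Worst corner, plotted | Cells changing colour |
|---|---|---|---|---|
| 8 v 19 | 3, 2 | 0.048 | 0.019 | 3 of 12, red to black |
| 7 v 19 | 4, 4 | 0.048 | 0.006 | 3 of 25, red to black |
| 8 v 17 | 2, 2 | 0.066 | 0.026 | 3 of 9, black to red |
| 9 v 19 | 3, 1 | 0.075 | 0.032 | 2 of 8, black to red |
| 6 v 19 | 1, 1 to 3, 3 | 0.004 to 0.016 | 0.002 to 0.003 | none |

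The last row is about the design rates: 10% and 30% of 62 are 6.2 and 18.6. In the 8 v 17 case, pooled proportion 0.25 merges two combinations at 0.0142 with two at 0.0403. The median is 0.027, and a favourable cell turns red.

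In the two scenarios of this table that go red to black, and in step 5, the sensitivity analysis that counts all missing outcomes as events stays below 0.025 (0.021, 0.008 and 0.016). It would not raise the alarm.

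**7. Wider grid.** The grid took 3 to 11 CSL312 events, up to 25 placebo events, a significant primary result and 1 to 4 missing per arm, which gives 1,456 cases. The worst corner was truly red in 464. In 275 of these (275/464 = 59%) the pooled rule coloured the whole graph black.

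**8. Covariates.** In runs with simulated covariates the direction at the worst corner was the same, for example own p 0.037 against a pooled median of 0.010.

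**The case against.** The strongest reply is that a per-cell median was meant. A graph with one axis per arm needs one value per coordinate. Subjects are treated as not interchangeable, so the natural reason for duplicates is that different subjects within an arm carry the imputed events. The fallback counts per-arm cells. The table can be read as a lesson in enumeration, and the remark about m > 1 as loose wording that fails only when there is one missing subject in each arm. The SAP also refers to an example graph that is not visible in the text available for this review, and it may show per-arm cells. Under this reading the worst corner is a single combination plotted with its own p-value, and nothing is distorted.

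Much of this stands. A reader might infer that the SAP definitely prescribes pooling, or that it is built to make results look robust. The documents support neither: the axes and the fallback point the other way, and pooling can also exaggerate fragility, as at 8 v 17 and 9 v 19. The graph is also a supportive display. There is one confirmatory test (SAP 10.3), and all the models are run whatever is plotted.

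What does not fall away is that the section never says which proportion is meant, and the text closest to the rule defines only the pooled one. Two programmers could follow it in good faith and produce graphs with different colours.

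**Conclusion.** SAP 10.1.3.1 is internally inconsistent and should be corrected before unblinding. Read with its own definition of m and its own table, the median rule pools over arms. Read with its axes and fallback, it works per cell. If per cell was intended, the table and the m > 1 sentence are wrong for it.

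Under the literal reading with missing outcomes in both arms, the worst corner is plotted with a smaller p-value than its own in the treatment-only model. This can make a result that tips look fully robust (0.026 plotted as 0.017; 0.048 as 0.006). A reader might infer that the rule always hides fragility. It does not: other cells can turn from black to red, and near the design rates with one to three missing per arm no colour changes.

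The illustrations rest on assumed event and missing counts and on a treatment-only model, whereas the SAP's model has covariates.

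**What to change.** State in SAP 10.1.3.1 that p-values are summarised only over combinations with the same pair: number imputed as events in CSL312 + SOC, and number imputed as events in placebo + SOC. Replace the table by one that shows counts per arm, for example the nine cells for a 2+2 split. Reword the m > 1 sentence to say that duplicates arise in a cell only when an arm has at least two missing subjects and some, but not all, of them are imputed as events.

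Replacing the median by another summary would not be enough, because the wrong combinations would still be merged. The cost is two sentences and one table. The 2^m models, the colours and the axes stay as planned.

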#### **10.1.4 Subgroup Analyses for Progression to Tracheal Intubation or Death Prior to Tracheal Intubation**

Subgroup analyses by the variables defined in Sections 8.2.7.1, 8.2.7.2, 8.2.7.3, 8.2.7.4, and 8.2.7.5 will be performed using the ITT Analysis Set as described above in Section 10.1.2. The logistic regressions will not include the factor for the respective subgroup analysis as independent variable (if applicable), but they will include the other covariates as specified for the primary analysis.

A forest-plot will be provided for the estimated risk difference and 95% CIs for each subgroup level.

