## 4.3 Randomization Procedures and Blinding

Randomization and blinding procedures are described in the protocol. Randomization will be conducted using an interactive response technology (IRT). Subjects will be randomly assigned to treatment with either CSL312 + SOC or placebo + SOC using a 1:1 randomization ratio and stratified by country (USA or Brazil). A centralized randomization schedule will be used. The randomization list will be generated according to the approved randomization specifications. The IRT service provider will keep the randomization code on file.

Study unblinding will take place after database lock, except in the situations as outlined in protocol sections 5.1.3.2, 5.1.3.3, and 5.1.3.4 related to emergency unblinding and unblinding for safety reasons.

Adequate procedures are in place to ensure the integrity of the blinded data within CSL. Study data will be provided to the IDMC as unblinded data.

The analyses planned for the IDMCs are described in a separate IDMC SAP.

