## 4.4 Determination of the Initial Sample Size

There are limited data on the rates of subjects with COVID-19 who progress to tracheal intubation or death prior to tracheal intubation within 28 days. For sample size calculation, a rate of 30% in the control group and a rate of 10% in the CSL312 group have been assumed. With a 1-sided  $\alpha = 0.025$  (which is equivalent to a 2-sided  $\alpha = 0.05$ ) and 1:1 randomization ratio for CSL312 + SOC versus placebo + SOC, a total of 124 subjects need to be randomized (62 subjects to CSL312 + SOC and 62 subjects to placebo + SOC) to achieve 80% power to show superiority using a 2 group chi-square test. For the sample size calculation, it is further confirmed using simulations performed in East 6.5 that 80% power is maintained, accounting for the interim analysis for futility and sample size re-estimation.

Depending on the results after the interim analysis, the sample size may be increased up to 248 subjects (124 subjects in CSL312 + SOC and 124 subjects in placebo + SOC).

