#### 10.2.2 Subgroup Analyses for Secondary Efficacy Endpoints

Subgroup analyses by the variables defined in Sections 8.2.7.1, 8.2.7.2, 8.2.7.3, 8.2.7.4, and 8.2.7.5 will be performed using the ITT Analysis Set as described in Section 10.2.1 for the following secondary endpoints:

- All-cause mortality;
- Incidence of tracheal intubation from randomization to Day 28;
- Clinical status assessed on an 8-point NIAID ordinal scale.

The logistic regressions will not include the factor for the respective subgroup analysis as independent variable (if applicable), but they will include the other covariates as specified for the primary analysis.

Forest-plots will be provided for the treatment comparison and 95% CIs for each subgroup level.

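### Subgroup effects are estimated separately in each level and never compared, so a uniform effect would look significant in one level only about half the time or more for each factor

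*SAP*

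**What the plan says.** SAP 10.1.4 plans subgroup analyses of the primary endpoint in the ITT set by sex, age group (below 65, 65 and over), comorbidity, use of anti-COVID-19 drugs and country. It refers back to SAP 10.1.2 for the method: Firth logistic regression with a 1-sided p-value judged at 0.025, and a covariate-adjusted risk difference with 95% CI. In the subgroup runs, "The logistic regressions will not include the factor for the respective subgroup analysis as independent variable", while the other covariates stay. For output, "A forest-plot will be provided for the estimated risk difference and 95% CIs for each subgroup level".

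SAP 10.2.2 applies the same scheme to mortality, intubation and NIAID status: "Forest-plots will be provided for the treatment comparison and 95% CIs for each subgroup level".

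A model that omits the subgroup factor can give level-specific estimates only if it is fitted separately in each level. No interaction or heterogeneity analysis appears in either document. SAP 10.3 names one confirmatory test and calls all others descriptive.

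**The concern.** A subgroup analysis is normally read as asking whether the effect differs between levels. The plan supplies the separate pieces, but no statistic that compares them. Readers will fill the gap by checking which levels reach significance or have an interval that excludes zero. That is a poor guide here, because the trial is sized for the whole population and each level has far less power. A significant result beside a non-significant one is then likely even when the effect is identical in both, and it could be taken as a reason to favour or exclude a group in later work.

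The plotted scale adds to this. The model is logistic but the plot shows risk differences, which change with baseline risk even when the odds ratio is constant. Protocol 1.1 names age over 65, obesity and diabetes as risk factors for severe disease, so differing baseline risks are plausible for at least the age and comorbidity factors.

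**Working it through.** **Inputs from the SAP.** Rates (4.4): "a rate of 30% in the control group and a rate of 10% in the CSL312 group have been assumed". Size (4.4): "62 subjects to CSL312 + SOC and 62 subjects to placebo + SOC". Test level (7): "Statistical tests will be 1-sided and will be performed at an alpha level of 0.025 unless otherwise stated". Subgroup splits are given nowhere, so 50/50 to 80/20 is an assumption, with equal allocation within levels.

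**1. The plan's own figure.** The target is "80% power to show superiority using a 2 group chi-square test". With pooled rate 0.20:

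n per arm = [1.96 × √(2 × 0.20 × 0.80) + 0.8416 × √(0.30 × 0.70 + 0.10 × 0.90)]² / 0.20² = (1.109 + 0.461)² / 0.04 ≈ 61.6, rounded up to 62. The plan's 124 is reproduced, with power 80.3%.

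**2. Power within a level, uniform effect.** For n per arm in a level:

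power = Φ[(0.20√n − 1.96 × √0.32) / √0.30]

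The two levels contain different subjects. With powers a and b, P(exactly one level significant) = a(1 − b) + b(1 − a).

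| Split, N = 124 | n per arm | a | b | Exactly one significant |
|---|---|---|---|---|
| 50/50 | 31, 31 | 0.50 | 0.50 | 50% |
| 60/40 | 37, 25 | 0.58 | 0.42 | 51% |
| 70/30 | 43, 19 | 0.64 | 0.33 | 55% |
| 80/20 | 50, 12 | 0.71 | 0.22 | 62% |

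At N = 248 the 50/50 split gives 2 × 0.803 × 0.197 = 32%. The 80/20 split (99 and 25 per arm) gives 0.946 × 0.579 + 0.421 × 0.054 = 57%. Exact and simulated values run slightly lower, so about 30-57% is a fair range. At N = 200 it is 41-62%. (Protocol 11.8 caps the increase at 200; Protocol 3.1 and SAP 4.4 say 248.)

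**3. At least one of five factors.** Simulation with unadjusted tests and independent factors, N = 124: 84% with all splits 50/50, 90% with splits from 60/40 to 80/20. Among trials significant overall: 88% and 96%. At N = 248: 61% with all splits 50/50, and about 72% with splits 60/40, 65/35, 70/30, 50/50 and 60/40.

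**4. Check under the planned model.** In 1,000 simulated trials with Firth regression and the SAP 10.1.2 covariates, using that last set of splits at N = 124, 52-57% were discordant per factor. At least one factor was discordant in 88%, or 94% given overall significance.

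**5. What a direct comparison would do.** Under the same uniform effect, an interaction test at 2-sided 0.05 flagged about 5% per factor unadjusted and 3-5% with Firth. For at least one of five, the range is about 12-23% (independent tests at exactly 5% give 1 − 0.95⁵ = 23%).

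**6. How weak that comparison is.** At 50/50 and N = 124, each level's risk difference has variance 0.30/31 = 0.00968, so its 95% CI half-width is 1.96 × √0.00968 = 19 points. The SE of the between-level difference is √(2 × 0.00968) = 0.139. Power for a 20-point difference in effect is Φ(0.20/0.139 − 1.96) = 30%. For 80% power the difference must be 2.80 × 0.139 = 39 points.

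**7. Scale.** The design odds ratio is (0.10/0.90)/(0.30/0.70) = 0.26. Applied to a placebo risk of 20%, it gives 6.1%, a risk difference of −14 points. Applied to 45%, it gives 17.5%, a difference of −27.5 points. The odds ratio is constant while the plotted effect doubles.

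**The case against.** Several points on the other side stand.

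- SAP 10.3 labels these tests descriptive, so no formal claim rests on them.
- SAP 10.1.4 names only risk differences and CIs as output. Within-level p-values follow from the reference to 10.1.2 but are not listed, and the table shells are a separate document.
- The intervals already carry information. Under a uniform effect at N = 124, the two levels' intervals fail to overlap in only about 0.7% of trials per factor.

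A reader might also infer four stronger things that the documents and figures do not support.

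- *A uniform effect will almost always look present in one level and absent in the other.* For a single factor the chance is 50-60%. Figures near 90% need any of five factors, and the highest also need overall significance. They should be set against 12-23% for interaction tests across five factors, not 5% for one.
- *Non-significant means no effect.* A zero or wrong-direction estimate in at least one level occurs in only 6% (50/50) to 16% (80/20) of trials per factor.
- *A log-odds interaction p-value settles the matter.* In step 7 it would be null by construction while the risk differences diverge, and the risk difference is the estimand in SAP 10.1.1.
- *Separate models lose much precision.* In a simulated level with 10 to 13 events, the joint model's log-odds-ratio error was only slightly smaller (0.86 v 0.89 and 0.80 v 0.82).

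**Conclusion.** The concern holds as a gap in reporting, not as an error in the primary analysis. SAP 10.1.4 and 10.2.2 give level-by-level effects with no comparison between levels, and reading significance across levels would mislead for a given factor in about 50-60% of trials at N = 124. This assumes a uniform 30% v 10% effect and splits between 50/50 and 80/20. The any-of-five figures also assume independent factors. Larger trials lessen the problem without removing it.

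One factor needs separate handling. SAP 8.2.7.4 defines anti-COVID-19 drug use by use during the trial, so it is partly determined after randomization, and an interaction test would not make it interpretable.

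This is a cheap improvement.

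**What to change.** Amend SAP 10.1.4:

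- For sex, age group, comorbidity and country, fit one Firth model per factor in the ITT set with the primary covariates, the subgroup factor and treatment-by-subgroup. Take the level-specific risk differences from it.
- For age, state whether the two-level term replaces continuous age or is added to it.
- Beside the forest plot, give the interaction estimate with 95% CI and p-value, and the between-level difference in risk differences with 95% CI, so that heterogeneity is also shown on the estimand's scale.
- Do not report within-level p-values.
- State that power is low (about 30% for a 20-point difference in effect at N = 124) and that a non-significant interaction is not evidence of a uniform effect.
- Present anti-COVID-19 drug use during the trial as descriptive only.

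Do the same for mortality and intubation in SAP 10.2.2.

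The cost is SAP wording and one model per baseline factor and endpoint. Data collection, sample size and the primary analysis are unchanged. The drawback is the weak interaction test, and several unadjusted ones will still sometimes flag a chance difference.
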